3.1.4 Exploratory Mechanistic Immunologic Studies

The immunologic mechanisms associated with a poor anti-spike protein antibody response after vaccination have not been studied in detail. We plan to explore the causes through a battery of immunologic assays. These detailed studies of T and B cells will be performed in a subset of patients to determine if specific alterations in immunity correlate with poor responsiveness to vaccination.

The following patients will have blood drawn for immunologic assays:

- 1) Initial responders (n=50):

- a. Patients who during screening have anti-SARS-CoV-2 spike protein antibody levels ≥ 250 ; one time point.
- 2) Low responders (n=50):
 - a. Patients who are low responders (anti-SARS-CoV-2 spike protein antibody >0 , but less than 250 U/ml) at screening.
- 3) Non-responders (n=50) with no change in immunosuppression:
 - a. Patients who have no detectable anti-SARS-CoV-2 spike protein antibody that are randomized to remain on their current immunosuppression.
- 4) Non-responders (n=50) with a reduction in immunosuppression:
 - a. Patients who have no detectable anti-SARS-CoV-2 spike protein antibody that are randomized to the immunosuppression adjustment arm.
 - b. Unlike the other patient groups, these subjects will have blood drawn for immunologic assessments at two time points; one prior to adjustment in their immunosuppression and a second performed 2 weeks after their immunosuppression is adjusted, but prior to receiving the Janssen Ad26.CoV2.S vaccine. This is intended to document any changes in immunologic profile secondary to immunosuppression adjustment.

Note, the immunologic assays will not be used for patient management or for decision-making in the trial. Thus, assays will be performed over the entire enrollment period until the target number of assays are performed. Patients receiving the Janssen Ad26.CoV2.S vaccine in Segment I will have anti-SARS-CoV-2 memory B cells and anti-SARS-CoV-2 T cell assays performed before and after vaccination. In addition to the tests described above, additional blood samples will be collected and stored for future testing. The details of the future tests will be outlined in a subsequent protocol amendment. The stored blood samples will not be analyzed until the protocol amendment is approved by the IRB.

Exploratory Mechanistic Study Lab Assessments.

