3.5 Secondary Study Assessments/Endpoints

- Any response in non-responders: Number and percentage of patients with undetectable anti-SARS-CoV-2 spike protein antibody level after 2 or more doses of mRNA vaccine who receive the Janssen Ad26.CoV2.S vaccine who develop anti-SARS-CoV-2 spike protein antibody levels >0 or <250 at 28 days.
- Good response in low-responders: Number and percentage of patients with anti-SARS-CoV-2 spike protein antibody levels >0 but <250 U/ml after 2 or more doses of mRNA vaccine who receive the Janssen Ad26.CoV2.S vaccine who develop anti-SARS-CoV-2 spike protein antibody levels ≥ 250 at 28 days.
- Segment II. Rate of achieving an anti-SARS-CoV-2 spike protein antibody level ≥ 250 U/ml 28 days after receiving the Janssen Ad26.CoV2.S vaccine in patients who failed to achieve the response in Segment I who received a second dose of the Janssen Ad26.CoV2.S vaccine after adjustment of immunosuppression.
- Durability of anti-SARS-CoV-2 spike protein antibody levels in patients who developed any level of antibody response after receiving the Janssen Ad26.CoV2.S vaccine at 180 days and/or between 1 and 2 years after receiving the Janssen Ad26.CoV2.S vaccine.
- Incidence of COVID-19 infection at 2 years.

Exploratory Endpoints (Mechanistic studies):

Baseline Differences

It is expected that at baseline (prior to receiving the Janssen Ad26.CoV2.S vaccine), when compared to responders, low responders and non-responders will demonstrate no SARS-CoV-2 specific T and B cells and lower mean number of T cell receptors. Non-responsiveness will correlate with lower mean numbers of T and B cells including specific subtypes such as T-helper cells and memory B cells.

Response to Alterations in Immunosuppression

Alterations in immunosuppression will lead to increased number of T and B cells from baseline. Paired t test with each patient serving as their own controls.

Additional Dose with the Janssen Ad26.CoV2.S Vaccine

Compared to those who do not respond, patients who respond to receiving the Janssen Ad26.CoV2.S vaccine will demonstrate new or increased levels of SARS-CoV-2-specific T and B cells. They also will have higher baseline levels of T cells, B cells, serum immunoglobulin levels and T cell repertoire.

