Adjustments will occur 2 weeks prior to receiving the Janssen Ad26.COVID-19 vaccine. In this arm, 50 patients who had T and B cell studies performed at baseline will have a second set of studies prior to receiving the Janssen Ad26.COVID-19 vaccine to determine the effect of immunosuppressive adjustment on these immune cells.

Screening study procedures can be completed at any time after consent up until the day of receiving the Janssen Ad26.COVID-19.

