6.1.2 Day -14 (+/-3 Days) Non-Responder Group Immunosuppression Change ONLY

Study team will contact the subject and document their immunosuppression medication and instruct the participant to begin their new immunosuppression medication regimen. Patient and graft status information will be recorded as well as the COVID-19 surveillance information collected.

For a subset of patients randomized to receive immunosuppression adjustment: prior to the adjustment the study team will send a kit for a local blood collection for Total Immunoglobulin levels and T-/B-cell immunophenotyping. These specimens will be shipped back to Mayo Rochester via overnight courier for testing.

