6.1.3 Baseline Visit (-4/+1 Day)

Subjects will return to Mayo Clinic for an in-person visit. Prior to receiving the Janssen Ad26.COVID-19 vaccine, the following study procedures will be performed:

- Serum pregnancy test for females of childbearing potential.
- Platelet count

- Mechanistic Studies
- Tacrolimus, Cyclosporine and MMF serum drug levels in subjects who are receiving these drugs or who were receiving these drugs at the time of enrollment.
- Anti-SARS-CoV-2 spike protein antibody and anti-SARS-CoV-2 nucleocapsid total antibody test
- The participant will have a nephrology consult and a complete physical exam (including review of concomitant medications and immunosuppression). The nephrologist will confirm with the IS reduction group that they have complied with their new medication regimen.
- Vital Signs (heart rate, blood pressure, temperature, pulse oximetry, height and weight).
- Asked if they are experiencing any COVID-19 symptoms or have been recently tested.

Eligible subjects will be vaccinated after these procedures have been completed. The following study procedures can be completed at any time during the visit:

- Study team will record concomitant medications and therapies.
- Study team will document immunosuppression medication
- Patient Status and Graft Status
- Risk Factor Assessment (see Section 14.5)
- Safety Follow Up Questionnaires (questions related to potential GBS, TTS, myocarditis and pericarditis symptoms)
- Kidney Transplant Follow-Up Questionnaire

To differentiate symptoms potentially related to the Janssen Ad26.COV2.S vaccine, the participant will be asked about any symptoms they may currently be experiencing prior to vaccination as well as after to differentiate potential vaccine related adverse events. Then they will receive the Janssen Ad26.COV2.S vaccine during a clinical appointment. All vaccination will be monitored post vaccine for 30 minutes for potential reactions to the vaccination.

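### Section 3.5 tests the effect of immunosuppression adjustment on T and B cells only as a before/after change within the adjusted arm, and the Day 0 samples in both randomized arms are not used to test it

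*Combined protocol and SAP*

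**What the plan says.** All references are to the combined protocol and SAP.

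- **Hypothesis and test (Section 3.5, exploratory endpoints).** "Alterations in immunosuppression will lead to increased number of T and B cells from baseline". The only method given is "Paired t test with each patient serving as their own controls".
- **Who has two pre-vaccination draws (Section 3.1.4).** The group listed as "Non-responders (n=50) with a reduction in immunosuppression" is drawn before the adjustment and again two weeks later, before vaccination: "Unlike the other patient groups, these subjects will have blood drawn for immunologic assessments at two time points".
- **How the change is to be read.** Section 3.1.4: "This is intended to document any changes in immunologic profile secondary to immunosuppression adjustment". Section 6.1.1 says that the second set of studies is done "to determine the effect of immunosuppressive adjustment on these immune cells".
- **Collection.** For Day -14, Section 6.1.2 says that "prior to the adjustment the study team will send a kit for a local blood collection", and the specimens go to Rochester by overnight courier. For Day 0, Section 6.1.3 says: "Subjects will return to Mayo Clinic for an in-person visit".
- **Day 0 assays in the other arm.** The table in Section 3.1.4 gives the non-responders without an immunosuppression change (also n=50) the same Day 0 immunoglobulin levels and T- and B-cell immunophenotyping.
- **Statistical methods (Section 6.8).** No test of the adjustment's effect on these assays is specified between arms. The section says in general terms that variables will be summarized by treatment group and compared for possible confounding.

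**The concern.** A paired t test removes stable differences between patients. It does not remove whatever else changes between the two draws. Here two things may change along with immunosuppression.

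The first is time. About two weeks pass, and no concurrent group is measured at both ends.

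The second is handling. The planned route is a local draw couriered overnight for Day -14, and a draw at a Mayo site for Day 0. Section 3.1.4 places the immunoglobulin and immunophenotyping laboratories in Rochester. A Rochester patient drawn locally at Day -14 therefore goes from shipped blood to on-site blood at the same moment that immunosuppression changes.

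At stake is one causal statement, that the adjustment altered the immune-cell profile. As written, it rests on a comparison without a control, although concurrent randomized patients have the same assays on Day 0.

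**Working it through.** **Which comparisons the schedule allows** (table in Section 3.1.4; Schedules of Events 2B and 2C)

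| Immunoglobulins and T/B-cell immunophenotyping | Day -14 | Day 0 |
|---|---|---|
| Non-responders, no change (n=50) | no | yes |
| Non-responders, adjusted (n=50) | yes | yes |

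The paired test can be run only in the second row. The Day 0 column gives a between-arm contrast with no extra draw. Timing is similar: Section 5.2.2 vaccinates the no-change arm two weeks after randomization and the adjusted arm two weeks after adjustment.

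**Inputs.** From the documents: 50 per group (Section 3.1.4) and two-sided alpha 0.05 (Section 6.7). The documents give no SD, effect size, correlation or power for this endpoint, so there is no stated figure to reproduce. Assumed for illustration: correlation ρ between Day -14 and Day 0 of 0.5 to 0.9, and a mean shift b unrelated to the adjustment of 0 to 0.5 cross-sectional SD.

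**Step 1. Error rate of the paired test when the adjustment does nothing.** In cross-sectional SD units, the SD of the change is √(2(1−ρ)). The paired t statistic has 49 degrees of freedom and noncentrality b·√50 / √(2(1−ρ)). For b = 0.2 and ρ = 0.8, the SD of the change is √0.4 = 0.632 and the noncentrality is 0.2 × 7.071 / 0.632 = 2.24, which gives a rejection rate of 59%. The full set, with nominal 5%:

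| Shift b (SD) | ρ = 0.5 | ρ = 0.7 | ρ = 0.8 | ρ = 0.9 |
|---|---|---|---|---|
| 0 | 5% | 5% | 5% | 5% |
| 0.1 | 11% | 15% | 20% | 34% |
| 0.2 | 28% | 43% | 59% | 87% |
| 0.3 | 55% | 77% | 91% | >99% |
| 0.5 | 93% | 99% | >99% | >99% |

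A shift in the opposite direction would hide a true rise in the same way.

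**Step 2. What the between-arm contrast does with the shift.** If the shift is common to both arms at Day 0, it cancels and the type I error stays at 5%. This requires the two subsets to be comparable, including in site mix.

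**Step 3. Sensitivity at 80% power.**
- Between arms, 50 against 50: (1.96 + 0.84) × √(2/50) = 2.80 × 0.20 = 0.56 SD by normal approximation, and 0.57 SD by noncentral t with 98 degrees of freedom.
- Paired, n=50: a standardized change of 0.404 by noncentral t. Multiplied by √(2(1−ρ)), this is 0.40 SD (ρ = 0.5), 0.31 (0.7), 0.26 (0.8) and 0.18 (0.9).

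For these correlations the paired test is the more sensitive one, which is a reason to keep it.

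**The case against.** The case for leaving the plan alone has five parts.

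- **The endpoint is exploratory.** Section 3.1.4 says that the assays will not guide patient management or trial decisions. This stands and limits the weight of the point.
- **The handling difference is not universal.** Section 6 allows remote visits to be done in person when convenient. Section 6.1.1 has vaccination at any of three centers, so Day 0 blood drawn in Arizona or Florida presumably also travels to Rochester. This stands: the contrast is clear only for Rochester patients drawn locally at Day -14. The lack of a comparator over time applies to every patient.
- **No artefact has been shown.** This also stands. Nothing in the documents says that overnight transport alters these assays, and the rejection rates above follow from assumed shifts.
- **The between-arm contrast has its own weaknesses.** A reader might infer that it is free of the handling bias. The documents do not support that. Randomization is stratified by number of mRNA doses and not by site, and Section 3.1.4 selects the mechanistic subsets by availability to have blood drawn. An imbalance in site mix would bring the same shift back in.
- **Section 6.8 already compares groups.** It does so for possible confounding. A descriptive Day 0 summary by arm could be read into it, but not a test of the adjustment's effect.

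A reader might also infer that this is the trial's only mechanistic evidence. It is not. Section 3.1.4 schedules ELISPOT, memory B-cell and neutralizing-antibody assays in both randomized arms at Day 0 and Day 28, and Section 3.5 also compares vaccine responders with non-responders.

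**Conclusion.** The point holds as a modest improvement to an exploratory analysis. The one test specified for the adjustment's effect on T and B cells is an uncontrolled before/after comparison, the documents read its result causally, and a concurrent randomized comparison of the same Day 0 assays is available but not specified.

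The size of any distortion cannot be stated from the documents. Under the assumed correlations, a shift of 0.1 SD would raise the false-positive rate of the paired test to 11% to 34%, and a shift of 0.2 SD to 28% to 87%. These figures show how exposed the test is; they do not show that this trial has such a shift.

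The between-arm contrast removes a time trend common to both arms. Because the subsets are chosen by availability, randomization protects it only in part. The primary, secondary and safety conclusions are unaffected.

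**What to change.** In Sections 3.5 and 6.8:

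1. Add a Day 0 comparison between the two randomized non-responder subsets (50 against 50) for immunoglobulins and T/B-cell immunophenotyping, adjusted for study site and prior-mRNA-dose stratum.
2. Report the baseline characteristics of the two subsets by arm, including site.
3. Keep the paired Day -14 to Day 0 analysis, but describe it as a before/after change. Make causal statements about the adjustment only where the between-arm comparison supports them.

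T-cell repertoire stays outside this comparison. The table in Section 3.1.4 has no Day 0 sample for it in either arm, although the text there describes collection from Day 0.

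**Cost.** The samples are already scheduled, so the work is plan wording and a small additional analysis. The price is sensitivity: about 0.57 SD at 80% power, against about 0.18 to 0.40 SD for the paired test at assumed correlations of 0.9 to 0.5. Comparing changes between arms would need a Day -14 draw in the no-change arm, collected in the same way. That is a new procedure and is not required for this fix.

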3.6 Primary Safety Endpoints

Primary Endpoint

SAEs related to the Janssen Ad26.CoV2.S vaccine.

Secondary Endpoints

1. SAEs related to reduction in immunosuppression.
2. Any hospitalization within 2 years of randomization.
3. Microbiologically defined infectious complications.
4. Patient survival at 2 years post randomization.
5. Graft survival at 2 years post randomization.
6. Adverse events related to the Janssen Ad26.CoV2.S vaccine.
7. Adverse events related to reduction in immunosuppression (rejection, graft loss, new onset donor-specific alloantibody formation).
8. Incidence of de novo alloantibody found as SOC.
9. Occurrence and relationship of SAEs and adverse events of special interest (AESIs), medically-attended adverse events (MAAEs) (until 6 months after the last Janssen vaccination), and MAAEs leading to study discontinuation (during the entire study) for all participants.

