1. To assess whether an anti-SARS-CoV-2 spike protein antibody level of ≥ 250 U/mL can be achieved 28 days after a dose of the Janssen Ad26.CoV2.S vaccine in kidney transplant recipients who did not form acceptable levels of anti-SARS-CoV-2 spike protein antibody (< 250 U/ml but > 0 U/mL) after receiving two or more doses of a mRNA vaccine: Pfizer-BioNTech (BNT162b2 vaccine) or Moderna (mRNA-1273). This includes any combination of the Pfizer-BioNTech (BNT162b2 vaccine) or the Moderna (mRNA-1273) results in two or more doses of mRNA vaccine.
2. To compare whether a dose of the Janssen Ad26.CoV2.S vaccine can achieve an anti-SARS-CoV-2 spike protein level ≥ 250 U/mL in kidney transplant recipients with no detectable anti-SARS-CoV-2 spike protein antibody after two or more mRNA vaccines. Kidney transplant recipients will be randomized to either maintenance of current immunosuppression or adjustment in immunosuppression around the time of receiving the Janssen Ad26.CoV2.S vaccine. The number of subjects with anti-SARS-CoV-2 spike protein level ≥ 250 U/mL between the two randomized groups will be compared.

Secondary Objectives

1. To determine the response* of the Janssen Ad26.CoV2.S vaccine in the a subset of patients who did not respond to an additional dose of the Janssen Ad26.CoV2.S vaccine in Segment I while on their maintenance immunosuppression. In this instance immunosuppression is adjusted (Segment II).
2. To determine the incidence of COVID-19 infection up to 2 years after enrollment or additional dose in all enrolled kidney transplant recipients (received Janssen Ad26.CoV2.S vaccine or not).
3. To determine the safety of an additional dose with the Janssen Ad26.CoV2.S vaccine after two or more doses of mRNA vaccine including vaccination with or without immunosuppression adjustment.

*Response is defined as achieving an anti-SARS-CoV-2 spike protein antibody level ≥ 250 U/ml 28 days after receiving the Janssen Ad26.CoV2.S vaccine.

Exploratory Objective

[figure not shown]
1. To perform exploratory in vitro assays to better understand mechanisms of response to COVID-19 vaccination.

3 Study Design

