This study is a phase III, prospective, open label clinical trial with one randomized arm. Its goal is to meet the unmet clinical need to provide vaccine induced immunity for our immunocompromised kidney transplant patients after receiving two or more doses of the Pfizer or Moderna COVID-19 vaccine (see Figure below for overview). Subjects will be pre-screened and interested qualified

subjects will be offered participation in this trial and, if applicable, consented. Once consented, serum levels of anti-SARS-CoV-2 spike protein antibody will be obtained. Patients with levels ≥ 250 U/ml will be followed for two years without receiving the Janssen Ad26.CoV2.S vaccine for clinical outcomes (COVID infection, graft and patient survival).

Study Schematic: Augmenting Anti-COVID Immunity In Transplant Recipients Via Heterologous Prime Booster Vaccination With Janssen Ad26.CoV2.S Vaccine

*Clinical endpoints include COVID-19 infection (primary endpoint) and secondary endpoints (hospitalization, infectious complications, patient survival, graft survival, significant AEs related to vaccine or to reduction in immunosuppression, de novo alloantibody)

** Exact cut-off still to be determined

Segment I

Patients with levels >0 but <250 U/ml of anti-SARS-CoV-2 spike protein antibody levels will receive one dose of the Janssen Ad26.CoV2.S vaccine. Their anti-SARS-CoV-2 spike protein antibody levels will be measured at multiple time points after receiving the Janssen Ad26.CoV2.S vaccine. Patients with undetectable anti-SARS-CoV-2 spike protein antibody levels (i.e. with levels = 0) will be randomized 1:1 (stratified by the number of mRNA doses received 2 vs 3) to receive the Janssen Ad26.CoV2.S vaccine and either: 1) continue on their current immunosuppression regimen or 2) have a transient immunosuppression medication adjustment prior receiving the Janssen Ad26.CoV2.S vaccine (described in Section 5.2.1).

Segment II

Patients in Segment I who received Janssen Ad26.CoV2.S vaccine while maintained on their usual immunosuppression medication dosage and did not reach the anti-SARS-CoV-2 spike protein antibody endpoint (≥ 250 U/ml) at 28 days will be offered an additional Janssen Ad26.CoV2.S vaccination. In this segment, immunosuppression will be adjusted (as described in Section 5.2.1)

and anti-SARS-CoV-2 spike protein antibody levels will be assessed at 28 days after the second vaccination with the Janssen Ad26.CoV2.S vaccine as the primary endpoint.

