3.1.1 Segment I

From the screened population, 100 kidney transplant recipients with an anti-SARS-CoV-2 spike protein antibody levels >0 but $<250\text{U/ml}$ (termed low responders) will receive an additional dose of the Janssen Ad26.CoV2.S vaccine. 300 kidney transplant recipients with undetectable anti-SARS-CoV-2 spike protein antibody levels (termed non responders) will receive an additional dose of the Janssen Ad26.CoV2.S vaccine after randomization 1:1 to either a continuation of their current immunosuppression regimen, or after immunosuppression adjustment as defined in Section 5.2.1.

The primary endpoint for Segment I is a SARS-CoV-2 spike protein antibody level $\geq 250\text{ U/ml}$ 28 days after vaccination. Anti- SARS-CoV-2 spike protein antibody levels along with anti-SARS-CoV-2 nucleocapsid antibody levels will be evaluated on days 14, 28, 90 and 180 days. If levels are detectable at Day 180, an additional sample collection will be obtained between one to two years after receiving the Janssen Ad26.CoV2.S vaccine.

- 1) Non-responders (n=300): These are patients who had no antibody response to their initial COVID mRNA vaccination (SARS-CoV-2 spike protein antibody = 0 U /mL). For this randomized portion involving non-responders, we will stratify patients so that we will have equal numbers of patients in each arm who have received 2 doses of mRNA vaccine and equal numbers that have received 3 doses of mRNA vaccine.
 - a. Randomization:
 - i. 150 subjects to receive Janssen Ad26.CoV2.S vaccine.
 - ii. 150 subjects to receive Janssen Ad26.CoV2.S vaccine AFTER immunosuppression adjustment as defined in “Immunosuppression Adjustment” section 5.2.1.
- 2) Low responders (n=100): Patients who had a demonstrable response to COVID mRNA vaccination but were below cutoff (SARS-CoV-2 spike protein antibody 0 to $<250\text{ U/mL}$) will receive the Janssen Ad26.CoV2.S vaccine.

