3.1.2 Segment II

In Segment I, 250 subjects will receive the Janssen Ad26.CoV2.S vaccine without immunosuppression adjustment (i.e. they will be maintained on their current immunosuppression). We expect that adjusting immunosuppression increases the response to the Janssen Ad26.CoV2.S vaccine compared to no adjustment. Thus, it is possible that patients from Segment I who were maintained on current immunosuppression, but did respond to receiving the Janssen Ad26.CoV2.S vaccine (i.e. they failed to reach the SARS-CoV-2 spike protein antibody cutoff (≥ 250 U/mL) at 28 days might respond if they underwent immunosuppression adjustment and receive a 2nd vaccination of using the Janssen Ad26.CoV2.S vaccine. A 2nd dose of the Janssen Ad26.CoV2.S vaccine will be offered to these patients. The approach will be similar to Segment I, in that the dose of the Janssen Ad26.CoV2.S vaccine will occur at 2 weeks after immunosuppression adjustment.

The number of patients in this segment could be anywhere between 0 and 250. There is no data to provide an estimate of enrollment, as it can be affected many factors. In prior studies of the mRNA vaccine, most of the low responders developed high levels of antibody after revaccination. If 50% of the non-responders are included here (n=75) and 25 low responders, then the number of subjects receiving the Janssen Ad26.COV2.S vaccine in Segment II would be 100.

Clinical follow-up will be for two years after receiving the Janssen Ad26.CoV2.S vaccine and analysis will focus on transplant specific outcomes (graft and patient survival, rejection episodes, etc.), general health outcomes (incidence of new diagnoses) and COVID specific outcomes (incidence of *de novo* SARS-CoV2 infection and clinical course/outcome).

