5.2.2 Janssen Ad26.CoV2.S Vaccine Dosing

There are no required medications pre or post vaccination with the Janssen Ad26.COV2.s vaccine. Dosage of study drug is defined as such:

- A single 0.5 mL dosage administered via an intramuscular injection. Typical administration time is less than a minute.

For Segment I, vaccination with the Janssen Ad26.COV2.s vaccine will occur 2 weeks post randomization in the no change in immunosuppression medication group (see Schedule of Events 2B). For those who will have an adjustment to their immunosuppression medication (see Schedule of Events 2C) vaccination with the Janssen Ad26.COV2.s vaccine will be 2 weeks after medication adjustment.

In Segment II, vaccination with the Janssen Ad26.COV2.s vaccine will occur three weeks after the result from the anti-SARS-CoV-2 spike protein test results which will be obtained on Day 28 of Segment I. On Day 42 the subject will begin immunosuppressive adjustment and the 2nd vaccination will be on Day 56.

There is no treatment for the Initial Responder group.

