5.3 Method for Assigning Subjects to Treatment Groups

Subjects will be placed in each group by their anti-SARS-CoV-2 spike protein antibody results obtained between screening and baseline:

Segment I

- Anti-SARS-CoV-2 spike protein antibody level >250 U/ml—no vaccination with the Janssen Ad26.CoV2.S vaccine, 2 year observation only
- Anti-SARS-CoV-2 spike protein antibody level >0, but <250 U/ml—vaccination with the Janssen Ad26.CoV2.S vaccine. If antibody levels remain <250 U/ml subjects will move to Segment II.
- Anti-SARS-CoV-2 spike protein antibody levels 0 U/ml—randomized to vaccination with the Janssen Ad26.CoV2.S vaccine with 1) no change in immunosuppression or 2) immunosuppression adjustment. For subjects that did not have a change in immunosuppression, if antibody levels remain <250 U/ml subjects will move to Segment II.

Segment II

- Study subjects from Segment I who received Janssen Ad26.CoV2.S without immunosuppression adjustment and their anti-SARS-CoV-2 spike protein antibody levels remain <250 U/ml, will be offered a second dose of the Janssen Ad26.CoV2.S vaccine with immunosuppression adjustment this time.

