We have performed power calculations using several different assumptions regarding the expected outcomes table below. For example, if we expect that the true response rate of 20% of patients without anti-S antibodies at baseline without an adjustment to their immunosuppression will achieve the primary endpoint after receiving the Janssen Ad26.COVID-19 vaccine, then a true response rate of 37% in the patients in the altered immunosuppression group will reject the null hypothesis of an equal response rate with 90% power. Thus, 120 patients will still have low levels (< 250 U/ml) and 30 will have high levels (≥ 250 U/ml). Of the 100 with low levels prior to receiving the Janssen Ad26.COVID-19 vaccine, we expect that >90 will develop high levels.

Response rate in arm with no alteration in immunosuppression	Response rate in arm with alteration in immunosuppression	Power	Significance level (alpha)
20%	60%	1.00	0.05

10%	24%	0.9	0.05
20%	37%	0.9	0.05
30%	48%	0.9	0.05
23%	40%	0.9	0.05
32%	50%	0.9	0.05
41%	60%	0.9	0.05
52%	70%	0.9	0.05
63%	80%	0.9	0.05

Because we expect a true response rate of 20% and 60% in the patients without and with immunosuppression alteration, respectively, we acknowledge that this study is over-powered for the current enrollment targets. If these were the true response rates, 30 patients would be required for each arm to achieve 90% power. Therefore, even if there is drop out and/or misestimation of the response rates within each category then this study will be sufficiently powered for this comparison.

All tests will be carried out using two-side hypothesis tests with a significance level of 0.05 unless otherwise noted.

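### Crossover into Segment II heavily dilutes any 2-year between-arm safety contrast for immunosuppression adjustment, and the plan pre-specifies no earlier randomized comparison

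*Combined protocol and SAP*

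**What the plan says.** Section 3.6 gives three secondary safety endpoints a two-year clock that starts at randomization: hospitalization (item 2), patient survival (item 4) and graft survival (item 5, "Graft survival at 2 years post randomization"). Secondary objective 3 in Section 2 asks for the safety of the additional dose, "including vaccination with or without immunosuppression adjustment".

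The randomized control arm in Section 3.1.1 is "150 subjects to receive Janssen Ad26.CoV2.S vaccine" with immunosuppression unchanged. Section 3, under Segment II, states that patients kept on their usual regimen who miss the antibody endpoint "at 28 days will be offered an additional Janssen Ad26.CoV2.S vaccination", this time with adjustment. Section 5.2.2 gives the timing: "On Day 42 the subject will begin immunosuppressive adjustment and the 2nd vaccination will be on Day 56". One bullet of Section 5.3 is firmer ("For subjects that did not have a change in immunosuppression, if antibody levels remain <250 U/ml subjects will move to Segment II"), but its Segment II bullet returns to an offer.

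Section 6.7, at a 20% control response, concludes: "Thus, 120 patients will still have low levels". Section 3.1.2 illustrates the uptake ("If 50% of the non-responders are included here (n=75) and 25 low responders") and allows Segment II to hold anywhere from 0 to 250 patients.

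Section 6.8 summarizes outcome variables across treatment groups and names no between-arm safety test. The only censoring rule, in Section 6.9, is last follow-up. No section handles Segment II entry or sets a safety comparison that ends before it.

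**The concern.** The randomized arms differ in immunosuppression adjustment only until controls begin Segment II. After that, many controls may have had the same adjustment, a few weeks later. Hospitalization, death and graft loss counted by arm to two years then pool a short period of clean contrast with a long period of mixed exposure, which pulls a true excess toward no difference. At stake is the interpretation: a reader who sees similar 2-year graft survival in the two arms could take it as evidence that adjustment is safe, when many of the comparison patients had also been adjusted.

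**Working it through.** **1. The plan's own figure.** Inputs: 150 controls (Section 3.1.1) and a 20% response (Section 6.7). 150 × (1 − 0.20) = 120, which reproduces the plan. It is the expected number eligible, not a ceiling and not an uptake. At a 10% response it is 150 × 0.90 = 135; at 30% it is 150 × 0.70 = 105; the maximum is 150.

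**2. Time before crossover.** Randomization falls at about Day −21 (Schedules of Events 2B and 2C) to Day −14 (Section 5.2.2, two weeks before vaccination). Time to Day 42 is 42 + 14 = 56 to 42 + 21 = 63 days. Of 730 days that is 56/730 = 7.7% to 63/730 = 8.6%. The adjusted arm's planned exposure, Day −14 to Day 28 (Section 5.2.1), is 42 days and lies wholly inside this period.

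**3. Dilution.** Let b be the 2-year risk without adjustment, d the true excess with adjustment, and f the share of controls adjusted in Segment II. If deferred adjustment carries the same excess:

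- adjusted arm: b + d
- control arm: b + f·d
- arm difference: (1 − f)·d

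| Controls adjusted | f | Share of d left |
|---|---|---|
| 0 | 0 | 100% |
| 75 (illustration in Section 3.1.2) | 75/150 = 0.50 | 50% |
| 120 (all eligible at 20% response) | 120/150 = 0.80 | 20% |
| 150 (all controls) | 1.00 | 0% |

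If all eligible controls accepted, 1 − 105/150 = 30% would remain at a 30% response and 1 − 135/150 = 10% at a 10% response.

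**4. Illustration of power, on assumed rates.** Section 1.5.9 says that the risk is unknown, so b and d below are assumptions. The method is the plan's arcsine scale: h = 2·asin√p₁ − 2·asin√p₂, power = Φ(|h|·√(150/2) − 1.96). For 20% versus 37% it gives 0.909, against the plan's 0.90.

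| Assumed b, d | None adjusted | 75 adjusted | 120 adjusted |
|---|---|---|---|
| 2%, 10 points | 0.96 | 0.32 | 0.08 |
| 5%, 10 points | 0.85 | 0.26 | 0.07 |
| 10%, 10 points | 0.69 | 0.21 | 0.06 |
| 2%, 5 points | 0.59 | 0.15 | 0.05 |
| 5%, 5 points | 0.38 | 0.12 | 0.05 |
| 10%, 5 points | 0.26 | 0.09 | 0.04 |

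For the second row, the comparisons are 5% versus 15%, 10% versus 15%, and 13% versus 15%. The shares in step 3 do not depend on b or d; the powers do.

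**The case against.** The best reply is that the plan never commits to this contrast. No between-arm safety test is named, and secondary objective 3 can be read as describing safety in each setting rather than estimating the effect of adjustment. Items 1 and 7 of Section 3.6 count events attributed to the reduction wherever they occur, so crossover would add to those counts rather than hide them. Under Section 1.5.9 the DSMB examines rejection and graft loss in all groups, and a 10% rejection rate pauses the study.

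Much of this stands. These safeguards still operate, but they are not arm comparisons. The attribution is made in an open-label trial, and the graded causality scale in Section 7.3.1 is worded for the vaccine. The 10% trigger is not a contrast between arms. Meanwhile Section 6.8 does summarize outcomes across treatment groups, and three endpoints run from randomization, so readers will see 2-year results by arm.

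A reader might infer more than the documents support:

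- **That the 2-year endpoints cannot show harm.** Half of an excess remains at the protocol's illustrative uptake. The contrast vanishes only if every control is adjusted.
- **That 80% of controls will be adjusted.** The bullet in Section 5.3 invites this, but the other places describe an offer. Footnote a of Schedule of Events 3 and Section 7.5 also remove some patients.
- **That rejection and new donor-specific antibody are diluted 2-year arm endpoints.** In item 7 they rest on attribution, with no two-year clock.

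**Conclusion.** The point holds as one of dilution and labelling. At the 20% planning response about 120 of 150 controls are offered the same adjustment from Day 42. A 2-year arm contrast on hospitalization, patient survival or graft survival then keeps about 50% of a true excess if 75 controls are adjusted and 20% if all 120 are.

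This rests on deferred adjustment carrying the same excess risk as immediate adjustment. Section 1.5.9 hypothesizes that low- and non-responders may be at low rejection risk; if the controls who cross over carry a smaller excess, the dilution is less. The calculation also ignores the second vaccine dose that those controls receive. The size of any harm, and hence the power, cannot be derived from the documents.

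The documents do not support saying that the trial would declare adjustment safe: no such decision rule exists. They do support saying that, as the plan stands, a null 2-year arm result would be weak evidence of safety, and that a cleaner randomized comparison is available but not specified.

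**What to change.** Three changes to the analysis plan:

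1. **Add an early randomized safety comparison.** Compare hospitalization, SAEs, rejection, graft loss and death by randomized arm, from randomization to a fixed cut-off that is the same in both arms and precedes any Segment II adjustment. The Day 42 visit has a window of ±7 days (Schedule of Events 3), so adjustment could begin at Day 42 − 7 = Day 35. A cut-off at Day 35 after the first study vaccination, counting events before any Segment II adjustment starts, covers the adjusted arm's planned six weeks. Include events between randomization and first vaccination: Section 7.3 sends those unrelated to study procedures to the medical history page, although the adjusted arm is already exposed from Day −14.
2. **Keep the 2-year by-arm results but relabel them** as immediate versus possibly deferred adjustment, and report Segment II exposure by arm.
3. **Treat exposure-based analyses as supportive only.** Censoring controls at Segment II entry, or modelling adjustment as time-varying, is open to bias because entry depends on Day 28 non-response.

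The cost is wording and a few tables, with no change to treatment, visits or sample size. Patient and graft status is already scheduled at Days 0, 14 and 28 in both arms. The downsides are fewer events in a short window, no capture of late graft loss, and donor-specific antibody data only where found in standard care (Section 3.6, item 8).
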